Prevalence of a second mesiobuccal canal in the mesial root of first and second maxillary molars is not clearly studied in Egyptian population. The prevalence rate will direct the attention of endodontists to its presence and will justify additional investigations to search for it.

Statement of the Problem

A high percentage of treatment failures is due to the impossibility of detecting the presence and location of the secondary mesiobuccal canal (MB2), located in the mesiobuccal root of the 1st maxillary molars and the 2nd maxillary molars (Blattner et al 2010), which prevents the correct implementation of biomechanical instrumentation, irrigation and obturation (Fig. 1).

[figure not shown]

Fig. 1

Maxillary molar with 4 canals: first mesiobuccal canal (MB1), secondary mesiobuccal canal (MB2), distobuccal canal (DB) and palatal canal (P). A Maxillary molar with joining mesiobuccal canals. B Maxillary molar with two separate mesiobuccal canals (Betancourt et al 2016)

deposited in the	e opening of the	canal and to	the difficulty	in visually ac	cessing
maxillary mola	rs.				

Review of literature

List of main databases used in search:

- Pubmed
- Google Scholar

Keywords:

- Second mesiobuccal canal - CBCT - Prevalence - Population

Maxillary first and second molars have been investigated because of their complex root and canal morphologies (Calis et al 1995; Ng et al 2001; Alavi et al 2002; Sert & Bayirli 2004; Weng et al 2009; Degerness & Bowles 2010; Neelakantan et al 2010; Zheng et al 2010; Kim et al 2012; Rouhani et al 2014; Silva et al 2014). According to previous results, most maxillary first molars exhibit 3 roots and 4 canals, including a mesiobuccal root with 2 canals and distobuccal and palatal roots with a single canal each (Zheng et al 2010; Neelakantan et al 2010; Sert & Baiyrli 2004; Lee et al 2011; Badole 2014).

Many studies investigated the morphology of the maxillary permanent molars focusing on the presence of a second mesiobuccal root canal in the mesial root (Pecora et al 1992; Sert & Bayirli 2004; Cleghorn et al 2006; Nikoloudaki et al 2015). They reported varying prevalence of the second mesiobuccal canal of maxillary first and second molars. Cleghorn et al 2006 found that the majority of maxillary first molars (95.9%) present 3 roots. The prevalence of a second mesiobuccal root canal in the mesial root varies between 26% (Pecora 1992) and 93.5% (Sert & Bayirli 2004). Nikoloudaki et al 2015 attributed these variations to the different methods that were used. The prevalence of two canals in laboratory studies is higher (60.5%) to that reported in clinical studies (54.7%) (Cleghorn et al 2006). From the previous studies, Nikoloudaki et al 2015 concluded that the incidence of the second canal (MB2) in the mesial root is higher than 50%. Ferguson et al 2005 report the presence of a third canal in the mesial root. Christie

et al 1991 in a retrospective study reported a second canal in the palatal root. **Badole et al 2012** found two individual palatal roots (mesiopalatal and distopalatal) with their own separate canals in one case. **Tian et al 2016** found additional canals in first and second molars in a Chinese Population using CBCT in 67.8% and 29.7% of mesiobuccal roots. They found also that the mesiobuccal root canal number showed bilateral symmetry between 79% of first molars and 82.3% of second molars, with a concurrence rate of 59.8% between adjacent molars.

Methods used to evaluate the inner morphology of a root:

Numerous methods have been used to examine root and canal morphologies, including:

- Histologic sections
- Canal staining and tooth clearing (Ng et al 2001)
- Sectioning (Weine et al 1969)
- Conventional and digital radiography (Pattanshetti et al 2008, Silva et al 2014)
- In vitro macroscopic examination (ex vivo using extracted teeth)
- Root canal treatment with magnification (Zheng et al 2010)
- The modified canal staining and clearing technique (Weng et al 2009)
- Computed tomographic imaging
- Contrast medium-enhanced digital radiography (Neelakantan et al 2010-2)
- Cone-beam computed tomographic (CBCT) imaging (Neelakantan et al 2010, Kim et al 2012 and Rouhani et al 2014).

Baratto Filho et al 2009 used three methods to evaluate the root canal morphology in maxillary first molars which are ex vivo, clinical, and cone beam computed tomography (CBCT) analysis and found that CBCT imaging was a useful diagnostic tool for this purpose as it can be used as a good method for initial identification of maxillary first molar internal morphology. It is also a non-

destructive tool which offers a higher spatial resolution at lower effective radiation doses and lower costs compared with computed tomographic imaging. In addition it provides a 3 dimensional images of root canal morphology assessment.

In vitro methodologies include various sectioning techniques (sectioning of the root perpendicular or vertically to the long axis of the tooth), root canal impression using low viscosity resin (Carns et al 1973), root canal staining, and tooth clearing as described by Vertucci 1984 and Barker et al 1969. A main drawback of these techniques is that the samples are irreversibly destructed, thus the results cannot be reproduced.

Clinical studies can evaluate the incidence of additional canals under magnification using loupes or dental operating microscope and by analyzing clinical patients' records or previously treated teeth (Stropko 1999). The above-mentioned techniques are unable to reveal in detail the irregularities of the root canal system owing to their inherent limitations. Information gained by peri-apical radiographic images are limited due to superimposition of adjacent teeth and hard tissues of the oro-facial region. Three-dimensional anatomic irregularities can be missed due to the two-dimensional depicting potential and the possible geometric distortion of the image (Patel et al 2007 and Cotton et al 2007).

Cone beam-computed tomography (CBCT) imaging techniques offer an effective way to overcome the above limitations. This is feasible by constructing detailed three-dimensional images of the teeth and the surrounding dental and alveolar structures. This information may be utilized for planning and intra-operative guidance (Nikoloudaki et al 2015).

Many studies analyzed the anatomic variations of maxillary molars using CBCT technology. **Nikoloudaki et al 2015** reported on the root and canal configurations of maxillary permanent molars in Greek population. In addition, several articles have used cone beam computed tomography (CBCT) to study the

morphology of the maxillary molars and to ascertain its ability to visualize the second mesiobuccal canal (MB2). **Betancourt et al 2016** have examined the geometric location in depth. They described in vivo the prevalence and location of the MB2 in the mesiobuccal root of the first maxillary molar (1MM) and the second maxillary molar (2MM) through CBCT imaging. In the 1MM protocol, the prevalence of the MB2 canal was 69.82% and was more frequent in women (p = 0.005). They concluded that CBCT is a high-precision diagnostic tool for not only detecting but also locating in vivo the MB2 canal in the mesiobuccal root of upper molars.

Aim of the Study

The aim of the study is to estimate the prevalence of a second mesiobuccal canal of maxillary first and second molars in Egyptian population.

Population: Egyptian population

Outcome Variable: Presence or absence of a second mesiobuccal canal of

maxillary first and second molars

	Outcome	Measuring Device	Measuring Unit	
	Measured			
Primary Outcome	Presence of a second mesiobuccal canal of maxillary first and second molars	CBCT Software (On Demand 3D®)	Binary System (Yes/No)	
Secondary Outcome	Prevalence in the whole sample (females and males)		Percentage	

Research question:

What is the percentage of presence of a second mesiobuccal canal in Maxillary First and Second Molars among Egyptian Population?

Materials and Methods

Study Design: Cross-sectional Study

Setting and Location:

- 1- The data collection will be obtained from the data base available at a private radiographic centre ORASCAN Oral & Maxillofacial Imaging Centre located in Cairo, Egypt.
- 2- CBCT images will be obtained from Egyptian patients who had CBCT examination as part of their dental examination, diagnosis or treatment planning during the years 2015-16-17.

Participants:

A total of 196 CBCT scans of Maxillary first and second permanent molars belonging to Egyptian individuals will be included.

Images of the first and second maxillary permanent molars are selected according to the following **Inclusion criteria:**

- First and second maxillary permanent molars of Egyptian patients starting from 15 years, males or females
- Intact roots without fractures or cracks
- Molars without posts or previous root canal treatment
- CBCT scans of maxillary first and second molars using 8 × 6 FOV, 0.2 voxel resolution

Exclusion criteria:

- Evidence of apicectomy or periapical surgery
- Odontogenic or non-odontogenic pathology
- Maxillary molars with developmental anomalies

- External or Internal Root resorption
- Canal Calcification
- Previous root canal treatment
- Extensive coronal restorations
- Posts or crown restorations
- Root caries specially reaching the trifurcation area
- Tomographic images of poor quality or artifacts interfering with the detection of root canals

Variables:

- 1. Number of root canals in mesiobuccal root of first and second maxillary molars
- 2. Sex of the patient will be identified and addressed as the prevalence of the second mesiobuccal canal may show sex predilection

Data Sources / Measurements:

Retrospective Data Analysis will be performed after the CBCT images are pooled from the computer database.

All the CBCT examinations were scanned using Cranex® 3D SOREDEX, 0.2 voxel resolution, 8 × 6 cm FOV, 90 kVp, 10 mA and 6 seconds exposure time.

CBCT images will be analysed in the 3 planes; first the sagittal and coronal sections will be oriented parallel to the long axis of the root, and then sections will be obtained on the axial plane for detection of the 2nd mesiobuccal canal (Betancourt et al 2016).

CBCT images will be interpreted by three oral radiologists independently; blinded from demographic data of the patients and from the results of each other.

Each one will evaluate the images separately twice with a period of two weeks between the two reading sessions.

Then inter-observational and intra-observational variability between the observers will be evaluated.

The sex of the patient will be identified from the patient's demographic data available on the patient's file on the database of the private radiographic centre.

Bias:

No source of bias.

Study Size:

The aim of the study is to assess the prevalence of a second mesiobuccal canal of maxillary first and second molars in Egyptian population. Based on the previous paper by Nikoloudaki et al, 2015, the prevalence of Second Mesiobuccal Canal of Maxillary First and Second Molars was 89 and 85%. Using a precision of 5, a design effect set at 1 with 95% CI (confidence interval), a total sample size of 196 will be sufficient. The sample size was calculated by Epi info.

Sampling Strategy: The sample will be collected by simple random sampling.

Quantitative Variables:

The number of CBCT scans of Egyptian individuals with second mesiobuccal canal will be counted to estimate the prevalence of the second mesiobuccal canal.

Statistical Methods:

- 1- Data will be analysed using IBM SPSS advanced statistics (Statistical Package for Social Sciences), version 21 (SPSS Inc., Chicago, IL). Numerical data will be described as mean and standard deviation or median and range. Categorical data will be described as numbers and percentages. Comparisons between male and females for normally distributed numeric variables will be done using the Student's t-test while for non-normally distributed numeric variables will be done by Mann-Whitney test. Comparisons between categorical variables will be performed using the chi square test. A p-value less than or equal to 0.05 will be considered statistically significant. All tests will be two tailed.
- 2- If the patient's age couldn't be found in the patient's file, the dental age will be used.
- 3- If the patient's sex couldn't be found in the patient's file, the patient's name will be used to indicate the sex. Patients with mixed name will be excluded.

References

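### The study is sized on a 95% confidence interval of ±5 points, but no interval is planned for the prevalence, and the scan count does not match the molar-level aim

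*Combined protocol and SAP*

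**What the plan says.** Aim of the Study sets an estimation objective: "The aim of the study is to estimate the prevalence of a second mesiobuccal canal", for maxillary first and second molars. The primary outcome is presence or absence of the canal in those molars, and the first item under Variables is the number of canals in the mesiobuccal root of each.

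Study Size takes its planning values from a Greek CBCT study ("the prevalence of Second Mesiobuccal Canal of Maxillary First and Second Molars was 89 and 85" percent) and reaches 196 as follows: "Using a precision of 5, a design effect set at 1 with 95% CI".

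Participants sets the sample in scans: "A total of 196 CBCT scans of Maxillary first and second permanent molars belonging to Egyptian individuals will be included". Quantitative Variables makes the scan the counted unit as well: "The number of CBCT scans of Egyptian individuals with second mesiobuccal canal will be counted".

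Statistical Methods, item 1, covers the binary outcome with "Categorical data will be described as numbers and percentages" and "Comparisons between categorical variables will be performed using the chi square test". Data Sources / Measurements adds inter- and intra-observer variability. The only confidence interval planned anywhere is the one in Study Size.

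**The concern.** A prevalence study has one main product, an estimate with its uncertainty. Here the uncertainty drives the sample size and then drops out of the analysis. Followed as written, the plan prints a percentage with no interval, and nothing shows whether ±5 points was reached.

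The unit belongs to the same point, because it decides both what is estimated and which interval is valid. A scan can show several molars. The plan gives no rule for turning them into one Yes/No, does not say whether one or both sides are read, and does not say whether first and second molars get separate prevalences. A single scan-level percentage would answer a different question from the one in the aim. If teeth are counted instead and a patient contributes more than one, both an ordinary binomial interval and the male-female chi-square test would treat correlated teeth as independent.

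**Working it through.** **Inputs.** From Study Size: prevalences 0.89 and 0.85 (read as first and second molars respectively), precision 5, design effect 1, 95% confidence (z = 1.96), n = 196. From Review of literature, on a Chinese CBCT study: "found additional canals in first and second molars in a Chinese Population using CBCT in 67.8% and 29.7% of mesiobuccal roots", with left-right symmetry of canal number of 79% (first molars) and 82.3% (second molars), and 59.8% concurrence between adjacent molars.

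**1. The plan's own figure.** n = z²p(1−p)/d², with d = 0.05:
- p = 0.85: 3.8415 × 0.1275 / 0.0025 = 195.9, so 196.
- p = 0.89: 3.8415 × 0.0979 / 0.0025 = 150.4, so 151.

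The figure of 196 therefore uses the more demanding planning value and treats 5 as a half-width (total width 10 points).

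**2. One observation per patient, 196 patients.** Half-width = 1.96√(p(1−p)/196):

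| p | half-width (points) |
|---|---|
| 0.89 | 4.4 |
| 0.85 | 5.0 |
| 0.678 | 6.5 |
| 0.50 | 7.0 (maximum) |

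Example of what is lost: 167/196 would be printed as 85.2%, while its Wilson 95% interval is 79.6% to 89.5%. There is no slack at 85%: 195 observations give 5.01 points and 180 give 5.2.

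**3. What a scan count estimates.** Assume one first and one second molar per scan, and a scan positive if either is.
- Lower bound: max(0.89, 0.85) = 89%.
- Under independence: 1 − 0.11 × 0.15 = 98.4%.
- Using the cited adjacent-molar concurrence, read as same-status agreement: with p₁ = 0.678, p₂ = 0.297 and a = P(both positive), agreement is 1 − p₁ − p₂ + 2a = 0.598, so a = 0.2865. The correlation is (0.2865 − 0.2014)/√(0.2183 × 0.2088) = 0.40. Carried to 0.89 and 0.85: a = 0.7565 + 0.40 × √(0.0979 × 0.1275) = 0.801, and P(any) = 1.74 − 0.801 = about 94%.

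**4. Both sides read in all 196 patients, teeth counted (assumption).** There are 392 teeth of each type and the design effect is 1 + ρ.
- At 0.85, half-width = 1.96√(0.1275(1 + ρ)/392): 3.5 points at ρ = 0 and 5.0 at ρ = 1. The ratio of the two is √2 = 1.41.
- From the cited symmetry s, ρ = 1 − (1 − s)/(2p(1−p)). For p = 0.678, s = 0.79: ρ = 0.52, effective n = 392/1.52 = 258. For p = 0.297, s = 0.823: ρ = 0.58, effective n = 392/1.58 = 249 (unrounded ρ).
- At these prevalences an interval ignoring clustering has half-width 4.6 and 4.5 points. The adjusted half-width is 5.7 for both.

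This assumes that the cited additional canals are second mesiobuccal canals and that symmetry in canal number stands for left-right agreement on presence.

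**5. If 196 meant teeth from fewer patients.** With two teeth per patient, p = 0.85 and an assumed intraclass correlation of 0.2 to 0.6, half-width = 1.96√(0.1275 × 1.2/196) = 5.5 up to 1.96√(0.1275 × 1.6/196) = 6.3 points.

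Steps 2, 4 and 5 are alternative readings and are not to be combined.

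**The case against.** The strongest reply is that the plan does name its unit: scans are enrolled and scans are counted, and a design effect of 1 fits one observation per scan. On that literal reading anyone can rebuild the interval from the count and 196, so the omission is one of reporting. This stands, and it limits the seriousness of the point. It does not remove the mismatch, because a scan count still has no positivity rule and still cannot supply the two molar prevalences that the aim asks for.

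A reader might infer three stronger things that the documents do not support:

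- **That 196 is wrong or too small.** It reproduces exactly from its own inputs. If both sides are read in all 196 patients, the effective samples of 258 and 249 exceed 196, so clustering within 196 patients does not make precision worse than one tooth per patient. Only the reading in which 196 counts teeth from fewer patients misses the target at 85%, and the plan does not say that.
- **That the reported interval will be too narrow by a factor of 1.41.** That needs both sides read, teeth counted, an unadjusted interval and perfect left-right correlation. The plan specifies none of these.
- **That a scan-level figure would be 98.4%.** That needs independence between adjacent molars. The cited 59.8% concurrence is well above the 42.8% expected under independence (1 − 0.975 + 2 × 0.678 × 0.297), so about 94% is the more plausible illustration. Only the lower bound of 89% is free of any assumption about correlation.

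**Conclusion.** The point holds as a low-cost improvement to the analysis and reporting, not as a sample-size error. No interval is planned for the estimate that the study exists to produce, and the stated counting rule does not deliver the molar-level prevalences in the aim.

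Its size depends on the reading. With one tooth of each type per patient, the target is met at both planning values and what is missing is the printed interval. Near the lower prevalences cited in the plan's own review, the half-width is about 6.5 points and the target is missed, which only a reported interval would reveal. With paired teeth, counts alone are not enough, and ignoring the pairing could make 5.7 points look like 4.6 or 4.5.

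Keeping 196 rests on 196 patients each contributing an eligible tooth of the type in question. Several exclusions (posts, previous root canal treatment, calcification) apply tooth by tooth, so this is not guaranteed. The number of molars per scan, the any-positive rule and the intraclass correlations are assumptions. The documents give none of them for this sample.

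**What to change.** In Quantitative Variables and Statistical Methods, replace the scan count with:

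> The prevalence of a second mesiobuccal canal will be estimated separately for first molars and for second molars, each with its denominator (eligible teeth and patients) and 95% CI: Wilson where each patient contributes one tooth to the estimate, or cluster-adjusted by patient where a patient contributes more than one tooth, including any pooled estimate. The male-female comparison will use the same unit and the same adjustment.

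State whether one or both sides are read. If a per-scan figure is also reported, label it as such and define when a scan is positive.

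In Study Size, add that the 5-point half-width holds at a prevalence of 85% or more if 196 patients each contribute an eligible tooth of the type; that 196 independent observations give about 6.5 points near 68% and at most 7.0; and that 196 teeth from fewer patients would give wider intervals.

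The cost is a patient identifier kept with each tooth and one extra results column. No extra scans are needed, and eligibility and the outcome hierarchy do not change. The unit and identifier are best settled before the images are read, since tooth-level pairing may be hard to recover from scan-level records.

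### The outcome is a property of the molar but the counting rule is per scan, and no method allows for several molars from one patient: a scan count would overstate molar prevalence, and an ordinary chi-square on molars would be oversized

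*Combined protocol and SAP*

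**What the plan says.** **Wording at molar level.** The aim, the research question and the primary outcome concern a second mesiobuccal canal in first and second maxillary molars. The eligibility criteria describe individual teeth. The first item under Variables is "Number of root canals in mesiobuccal root of first and second maxillary molars". Study Size plans from a Greek CBCT study in which "the prevalence of Second Mesiobuccal Canal of Maxillary First and Second Molars was 89 and 85" percent.

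**Wording at scan level.** Participants states: "A total of 196 CBCT scans of Maxillary first and second permanent molars belonging to Egyptian individuals will be included". Quantitative Variables states: "The number of CBCT scans of Egyptian individuals with second mesiobuccal canal will be counted", and this count is to give the prevalence.

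**Sample size.** "Using a precision of 5", with "a design effect set at 1 with 95% CI (confidence interval), a total sample size of 196 will be sufficient".

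**Analysis.** Statistical Methods, item 1: "Comparisons between categorical variables will be performed using the chi square test". Tests are two-sided at 0.05. No clustered or paired method appears. Sex is the second item under Variables, listed because prevalence may differ by sex.

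**Evidence of clustering.** The Review of literature reports a Chinese CBCT study with additional canals in 67.8% of first-molar and 29.7% of second-molar mesiobuccal roots. There, canal number "showed bilateral symmetry between 79% of first molars and 82.3% of second molars, with a concurrence rate of 59.8% between adjacent molars".

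**Not stated.** The protocol does not say how many molars per scan are read, whether one or both sides are used, how several molars become one scan result, or whether the sex comparison is made on molars or on scans.

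**The concern.** One scan can supply up to four eligible molars: first and second, left and right. The text leaves two routes from molars to a prevalence, and each has a problem.

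- **Count scans.** With no rule for combining molars, the natural reading is that a scan is positive if any molar is. That estimates a different and larger quantity than the prevalence per molar, which is what the aim and the 89% and 85% refer to.
- **Count molars.** The only test named assumes independent observations, while the protocol's own literature review reports strong agreement within patients. Intervals would be too narrow and the male/female test would reject too often. Sex is one of only two declared variables, so a spurious sex difference could become a main result.

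**Working it through.** **Inputs.** Planning rates 0.89 and 0.85, precision 5 (read as percentage points), 95% confidence, design effect 1 and N = 196 (Study Size). Rates 0.678 and 0.297, left-right agreement 0.79 and 0.823, and adjacent concurrence 0.598 (Review of literature).

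**1. The plan's own figure.** n = 1.96² × p(1−p) / 0.05². At p = 0.85 this is 195.9, so 196: reproduced. At p = 0.89 it is 151.

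**2. Correlations implied by the cited agreement.** For left and right, ρ = 1 − (1 − agreement) / [2p(1−p)].
- First molars: 1 − 0.21 / (2 × 0.678 × 0.322) = 0.52.
- Second molars: 1 − 0.177 / (2 × 0.297 × 0.703) = 0.58.
- Adjacent molars, if concurrence means simple agreement: P(both) = (0.678 + 0.297 − 1 + 0.598) / 2 = 0.2865; covariance = 0.2865 − 0.678 × 0.297 = 0.085; ρ = 0.085 / √(0.2183 × 0.2088) = 0.40.

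**3. Any-positive scan count.** For two same-type molars at 85%, P(at least one) = 1 − (0.15² + ρ × 0.85 × 0.15). With ρ = 0.52 this is 91.1%; with ρ = 0.58 it is 90.4%. The excess over 85% is 5 to 6 points, at least as large as the planned precision of 5.

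**4. Molar-level analysis.** Design effect (DEFF) = 1 + (m − 1)ρ for m molars per patient. The actual size of a nominal 5% test is 2[1 − Φ(1.96/√DEFF)].

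| Molars analysed | DEFF | Sex-test false-positive rate |
|---|---|---|
| One value per scan | 1 | 5% |
| Both sides of one tooth type, all patients | 1.52 to 1.58 | 11.2 to 11.8% |
| Both sides in half the patients, one side in the rest | 1.35 to 1.38 | 9.1 to 9.6% |
| One adjacent pair per patient | 1.39 to 1.40 | 9.6 to 9.7% |
| Four molars pooled, margins 89% and 85% | 1.94 to 2.33 | 16 to 20% |

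In the half-and-half row, DEFF = (0.5 + 0.5 × 2(1 + ρ)) / 1.5. The four-molar range takes the correlation between a first molar and the opposite second molar, which the protocol does not give, as 0 at one end and 0.40 at the other.

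For two same-type molars, the naive 95% interval covers 88 to 89% by the formula and 87 to 89% by simulation. Simulating the sex test under the null with 98 patients per sex at 85% prevalence gave 11.4% (ρ = 0.52) and 11.6% (ρ = 0.58).

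**5. Precision with 196 scans.** Both sides of one tooth type give 392 molars and an effective n of 392/1.58 = 249 to 392/1.52 = 258. At 85% the naive half-width is 1.96 × √(0.1275/392) = 3.5 points. The correct one is 3.5 × √1.52 to 3.5 × √1.58, about 4.4 points, so the 5-point target is met.

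**The case against.** The strongest reply is that the protocol never commits to treating molars as independent. It samples scans and says that it counts scans. For one value per scan, a design effect of 1 and an ordinary chi-square are both correct. This stands, and it rules out three stronger readings that a reader might infer:

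- **That the design effect of 1 is an error.** It is right for the unit that is sampled and counted.
- **That 196 is too few.** With 196 scans, precision stays within 5 points even with clustering. It would miss the target (6.2 to 6.3 points at two molars per patient) only if 196 were a count of molars, and Participants says scans.
- **That the sex test's error rate more than doubles as planned.** That needs nearly all patients to supply both sides of a tooth type, or four molars each. The protocol does not say that both sides are read, and exclusions for restorations, root caries, calcification and previous treatment will break some pairs.

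The correlations are also open to challenge. They come from a brief summary of one study with lower rates. The symmetry figure concerns canal number rather than presence or absence, and the 0.40 depends on how concurrence was defined. In addition, Statistical Methods specifies no prevalence interval and names no first-versus-second molar comparison.

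The reply does not remove the gap. The scan count has no rule for combining molars and, read as any-positive, does not estimate molar prevalence. Results comparable with 89% and 85% need molar-level tables, and the only test offered for those ignores clustering.

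**Conclusion.** The concern holds in conditional form. The unit of analysis is unsettled, and either reading does harm unless the plan is completed. An any-positive scan count would report about 90 to 91% where molar prevalence is 85%. A naive molar-level analysis with both sides read would give intervals covering about 87 to 89% and a sex test with a true size of about 11 to 12%. That size falls to about 9 to 10% when half the patients supply both sides or each supplies one adjacent pair, and rises to about 16 to 20% with four molars pooled.

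These figures assume that the cited agreement can be treated as agreement on presence or absence, that it carries over to Egyptian patients at 85 to 89% prevalence, and that patients contribute equal numbers of molars except where stated. The left-right values (0.52 and 0.58) are firmer than the adjacent value (0.40). The documents do not support a larger sample or a finding that the stated design effect is wrong.

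**What to change.** **Study Size and Quantitative Variables.** Keep the 196-scan calculation. State that the patient (one scan each) is the sampling unit, that prevalence is reported separately for first and second molars at molar level, and which sides are read. If a per-patient prevalence is also wanted, define how molars combine into it and label it as a different quantity.

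**Statistical Methods, item 1.** For every molar-level interval and comparison (male/female, and first/second molar if made), replace the ordinary chi-square with a method that treats the patient as the cluster. This can be a binomial GEE with logit link, robust standard errors and patient as subject, or a Rao-Scott chi-square. Keep the ordinary chi-square only for tables with one value per patient.

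**Cost.** A few sentences and slightly more analysis work, with no extra scans or readers. With both sides read, molar-level prevalence intervals become about 23 to 26% wider than the naive ones (√1.52 = 1.23, √1.58 = 1.26).

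### Does the plan leave observer agreement to a chi-square test, and the yes/no outcome undefined across six readings per image?

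*Combined protocol and SAP*

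**What the plan says.** Data Sources / Measurements describes the readings: "CBCT images will be interpreted by three oral radiologists independently; blinded from demographic data of the patients and from the results of each other". It continues: "Each one will evaluate the images separately twice with a period of two weeks between the two reading sessions". That makes 3 × 2 = 6 readings per image. The same section then says: "Then inter-observational and intra-observational variability between the observers will be evaluated". No statistic is attached to that sentence.

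The outcome table under Aim of the Study gives the primary outcome as "Presence of a second mesiobuccal canal of maxillary first and second molars", scored yes or no. Quantitative Variables says that scans showing the canal will be counted. It does not say whose reading, or which session, decides.

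Statistical Methods names the t-test and Mann-Whitney test for numeric comparisons between the sexes. It then says: "Comparisons between categorical variables will be performed using the chi square test". The threshold is "A p-value less than or equal to 0.05 will be considered statistically significant". The section also has categorical data described by counts and percentages. Kappa, McNemar's test and percent agreement appear nowhere in the document.

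**The concern.** Observer variability on a yes/no call is a paired agreement problem, and a chi-square test does not address it. Laid out as a reader-by-reader table, chi-square tests whether the two sets of calls are unrelated, so it can be significant when agreement is only a little above chance. With the readers treated as two separate groups, it ignores that both saw the same scans and can miss a systematic difference between them. If chi-square were the tool for this analysis, the plan's check on reading error would be uninformative.

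The second worry is the outcome itself. When the six readings differ, the protocol does not say which one enters the prevalence. Study Size plans a precision of 5 points, so a choice that moved the estimate by several points would matter, and an unfixed choice could be made after the results are known.

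**Working it through.** **Inputs from the protocol.** 196 scans (Participants, Study Size); prevalence 85% and 89%, precision 5, 95% confidence, design effect 1 (Study Size); 3 readers × 2 sessions (Data Sources / Measurements); two-sided 0.05 (Statistical Methods). The reader tables and reader accuracies below are assumptions, because the documents give none. They take one call per scan, which the protocol does not settle.

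**The plan's own figure.** n = 1.96² × p(1 − p) / d². With p = 0.85 and d = 0.05, n = 3.8415 × 0.1275 / 0.0025 = 195.9, so 196. The stated size reproduces, and the present question does not affect it.

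**Chi-square as a test of association between readers.** Take two readers with 167 of 196 positive each (85.2%): 147 both yes, 20 and 20 discordant, 9 both no.

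- Raw agreement = (147 + 9)/196 = 0.796.
- Chance agreement = (167/196)² + (29/196)² = 0.748.
- Kappa = (0.796 − 0.748)/(1 − 0.748) = 0.19.
- Pearson chi-square = 7.12, p = 0.0076 (0.017 with continuity correction; Fisher 0.019).

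With equal reader totals, chi-square = n × kappa², so the uncorrected test reaches 0.05 once kappa is 1.96/√196 = 0.14. The test is plainly unsuited to agreement.

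The p-value depends heavily on the assumed cells. Keeping 40 disagreements split 20/20:

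| Both no | Kappa | Uncorrected p |
|---|---|---|
| 5 | 0.08 | 0.245 |
| 6 | 0.11 | 0.113 |
| 9 | 0.19 | 0.0076 |
| 13 | 0.27 | 0.0002 (rounded up from 0.00015) |

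**Chi-square as a comparison of two reader groups.** 167 against 155 positive is a gap of 12/196 = 6.1 points; unpaired p = 0.11. Exact McNemar on the same gap depends on the discordant split: 0.0075 at 15/3, 0.036 at 20/8, 0.050 at 22/10, 0.081 at 26/14. With the higher reader at 182 of 196, the unpaired uncorrected test gives 0.045. So the contrast between the two tests is real in some tables and absent in others.

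**Does the plan apply chi-square to readers?** In Statistical Methods the chi-square sentence comes straight after the two tests for males versus females. The Variables section names sex as the factor that may relate to the canal's presence. Males and females are independent groups, so chi-square fits there. The observer evaluation sits in Data Sources / Measurements, with no cross-reference to any test. The natural reading is that chi-square serves the sex comparison and that the agreement statistic was left unnamed.

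**Size of the combining choice.** Let p be the true prevalence and a = sensitivity = specificity, with independent errors. A single reading gives p·a + (1 − p)(1 − a). A two-of-three majority gives p·f(a) + (1 − p)·f(1 − a), where f(x) = x³ + 3x²(1 − x).

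| p | a | Single | Majority | Difference (points) |
|---|---|---|---|---|
| 0.85 | 0.95 | 81.5% | 84.5% | 3.0 |
| 0.85 | 0.90 | 78.0% | 83.0% | 5.0 |
| 0.6982 | 0.95 | 67.8% | 69.5% | 1.7 |
| 0.6982 | 0.90 | 65.9% | 68.7% | 2.9 |

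The 0.6982 is the first-molar prevalence from an earlier CBCT study cited in the protocol's literature review. At p = 0.85, correlated reader errors shrink the difference to 1.1–1.9 points at correlation 0.3 and 0.5–0.8 at 0.5. With sensitivity 98% and specificity 85% under independent errors, it is 85.81% − 85.55% = 0.3 points. In the four tabulated cases the majority lies closer to the true value.

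**The case for a change.** The strongest case for a change does not need the chi-square argument. A planned analysis has no stated statistic, and the primary outcome has no rule when readings conflict. The Bias section claims there is no source of bias, so the observer evaluation is the plan's only measurement of reading error. Naming kappa and a combining rule would cost a sentence or two and no extra readings. Fixing the rule in advance would also stop the choice from being steered by the results.

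Both omissions are real, and no redaction explains them. The point about fixing the rule in advance is fair as good practice.

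It does not, however, turn an omission into an error. Three independent readers with a repeat session is a standard layout for an agreement study, and the data it yields support kappa, raw agreement and paired comparisons without any change to design. Raw agreement is itself a percentage, which Statistical Methods already provides for. A majority or consensus of the readers is the usual way to settle such calls, and an odd number of readers makes a majority of the first session always available. Kappa would need cautious reading in any case: at 85% positives, 79.6% raw agreement gives kappa 0.19, while the prevalence-adjusted value is 2 × 0.796 − 1 = 0.59.

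**Conclusion.** The concern does not call for a change. Chi-square would be the wrong tool for observer agreement, but the plan does not say it will be used for that, and for comparing males and females it is suitable. The p-values that make the problem look sharp rest on chosen cells and change sides of 0.05 under other plausible splits.

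What is left is missing detail: an unnamed agreement statistic and an unstated rule for combining six readings. Analysts can be expected to fill both sensibly from readings already planned, and the sample size of 196 is unaffected. The effect of the combining choice is about 0.3 to 5 points. It reaches the planned precision of 5 only with 85% prevalence, 90% reader accuracy and fully independent errors. Those accuracies are assumptions, so the documents do not establish a material effect on the reported prevalence.
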